3.3. Other Endpoint(s)

Not applicable.

PFIZER CONFIDENTIAL

The official version of this form is located in the electronic document management system.

3.4. Baseline Variables

The baseline value for laboratory, 12-Lead ECG and vital signs is defined as the latest measurement prior to taking dose.

3.5. Safety Endpoints

3.5.1. Adverse Events

Any events occurring following start of treatment will be counted as treatment emergent.

3.5.2. Laboratory Data

Safety laboratory tests will be performed as described in the protocol.

To determine if there are any clinically significant laboratory abnormalities, the hematological, clinical chemistry (serum) and urinalysis safety tests will be assessed against the criteria specified in the sponsor reporting standards. The assessment will not take into account whether each subject's baseline test result is within or outside the laboratory reference range for the particular laboratory parameter.

4. ANALYSIS SETS (POPULATIONS FOR ANALYSIS)

Data for all participants will be assessed to determine if participants meet the criteria for inclusion in each analysis population prior to unblinding and releasing the database and classifications will be documented per standard operating procedures.

Participant Analysis Set	Description
Safety Analysis Set	All randomized participants who received at least 1 dose of the study intervention
PK Concentration Set	All randomized participants who received at least 1 dose of study intervention and at least 1 concentration value is reported
PK Parameter Set	All randomized participants who received at least 1 dose of study intervention and at least 1 of the PK parameters is calculated
Immunogenicity Analysis Set	All randomized participants who received at least 1 dose of study intervention with at least 1 post-treatment anti-drug antibody determination

5. GENERAL METHODOLOGY AND CONVENTIONS

5.1. Hypotheses and Decision Rules

There are no statistical hypotheses for this study.

PFIZER CONFIDENTIAL

The official version of this form is located in the electronic document management system.

5.2. General Methods

No formal statistical tests will be performed. Descriptive summaries will be provided for all endpoints by treatment group.

5.2.1. Analyses for Binary Endpoints

Not applicable.

5.2.2. Analyses for Continuous Endpoints

Not applicable.

5.2.3. Analyses for Categorical Endpoints

Not applicable.

5.2.4. Analyses for Time-to-Event Endpoints

Not applicable.

5.3. Methods to Manage Missing Data

5.3.1. Pharmacokinetic Concentrations

Concentrations below the limit of quantification

In all data presentations (except listings), concentrations below the limit of quantification (BLQ) will be set to zero. In the listings BLQ values will be reported as “<LLQ”, where lower limit of quantification (LLQ) will be replaced with the value for the lower limit of quantification.

Deviations, missing concentrations and anomalous values

Subjects who experience events that may affect their PK profile (eg, due to known loss of drug during IV administration) may be excluded from the PK analysis.

In summary tables and plots of mean and median profiles of PK, statistics will be calculated having setting concentrations to missing if one of the following cases is true:

1. A concentration has been collected as ND (ie, not done) or NS (ie, no sample);
2. A deviation in sampling time is of sufficient concern or a concentration has been flagged anomalous by the PK analyst.

Note that summary statistics will not be presented at a particular time point if more than 50% of the data are missing.

PFIZER CONFIDENTIAL

The official version of this form is located in the electronic document management system.

5.3.2. Pharmacokinetic Parameters

Actual PK sampling times will be used in the derivation of PK parameters.

If a PK parameter cannot be derived from a subject's concentration data, the parameter will be coded as NC (ie, not calculated). (Note that NC values will not be generated beyond the day that a subject discontinues).

In summary tables, statistics will be calculated by setting NC values to missing; and statistics will not be presented if more than 50% of the data are NC.

If an individual subject has a known biased estimate of a PK parameter (due for example to an unexpected event such as incomplete SC injection), this will be footnoted in summary tables and will not be included in the calculation of summary statistics or statistical analyses.

6. ANALYSES AND SUMMARIES

6.1. Pharmacokinetic Analysis

6.1.1. Pharmacokinetic Parameters

The PK parameters for PF-06823859 following single dose administration will be derived from the concentration-time profiles by noncompartmental analysis and summarized descriptively.

The PK parameter analysis will be carried out with PK parameter analysis set.

Calculation of PK parameters

Parameter	Definition	Method of determination
C_{max}	Maximum serum concentration	Observed directly from data
$C_{max} (dn)$	Dose normalized C_{max}	$C_{max}/dose$
T_{max}	Time at which C_{max} occurs	Observed directly from data as time of first occurrence
AUC_{inf}^a	Area under the serum concentration-time profile from time zero extrapolated to infinite time	$AUC_{last} + (C_{last}^*/k_{el})$, where C_{last}^* is the predicted serum concentration at the last quantifiable time Point estimated from the log-linear regression analysis
$AUC_{inf} (dn)^a$	Dose normalized AUC_{inf}	$AUC_{inf}/Dose$
AUC_{last}	Area under the serum concentration-time profile from time zero to the time of the last quantifiable concentration (C_{last})	Linear/Log trapezoidal method
$AUC_{last} (dn)$	Dose normalized AUC_{last}	$AUC_{last}/Dose$
AUC_{14day}	Area under the concentration-time profile from time zero to 14 days post-dose (336 hours)	Linear/Log trapezoidal method

PFIZER CONFIDENTIAL

The official version of this form is located in the electronic document management system.

Parameter	Definition	Method of determination
AUC _{28day}	Area under the concentration-time profile from time zero to 28 days post-dose (672 hours)	Linear/Log trapezoidal method
t _{1/2} ^a	Terminal half-life	Log _e (2)/k _{el} , where k _{el} is the terminal phase rate constant calculated by a linear regression of the log-linear concentration-time curve
CL ^a	Clearance	Dose/AUC _{inf}
V _z	Volume of distribution	Dose/(AUC _{inf} *k _{el})
MRT ^a	Mean residence time	AUMC _{inf} / AUC _{inf} - DOF/2, where AUMC _{inf} is the area under the moment curve from time 0 extrapolated to infinity and DOF is the duration of the IV infusion.

a. if data permitted

Actual PK sampling times will be used in the derivation of PK parameters. In the case that actual PK sampling times are not available, nominal PK sampling times will be used in the derivation of PK parameters.

Summary statistics will be provided for these PK parameters as summarized below:

Parameter	Summary statistics
AUC _{last} , AUC _{last} (dn), AUC _{inf} , AUC _{inf} (dn), AUC _{14day} , AUC _{28day} , C _{max} , C _{max} (dn), CL, V _z , MRT	N, arithmetic mean, median, coefficient of variation (CV)%, standard deviation (SD), minimum, maximum, geometric mean and geometric CV%.
T _{max}	N, median, minimum, maximum.
t _{1/2}	N, arithmetic mean, median, CV%, SD, minimum, Maximum.

Box and whisker plots for individual subject parameters (AUC_{last}, AUC_{last}(dn), AUC_{inf}, AUC_{inf}(dn), AUC_{14day}, AUC_{28day}, C_{max} and C_{max}(dn)) will be presented and overlaid with geometric means.

6.1.2. Pharmacokinetic Concentrations

Presentations for PF-06823859 concentrations will include:

- a listing of all concentrations sorted by subject ID and nominal time postdose. The concentration listing will also include the actual times. Deviations from the nominal time will be given in a separate listing.
- a summary of concentrations by nominal time postdose, where the set of statistics will include n, mean, median, SD, CV, minimum, maximum and the number of concentrations above the LLQ.

PFIZER CONFIDENTIAL

The official version of this form is located in the electronic document management system.

- Median concentrations time plots (on both linear and semi-log scales) against nominal time postdose.
- Mean concentrations time plots (on both linear and semi-log scales) against nominal time postdose.
- Individual concentrations time plots (on both linear and semi-log scales) against actual time postdose.
- Individual concentrations time plots by participant (on both linear and semi-log scales) against actual time postdose (there will be separate plots for each participant per scale).

The length of time used for the x-axes of these plots will be decided on review of the data, and will depend on how long PF-06823859 concentration is quantifiable in the matrix. For summary statistics, median and mean plots by sampling time, the nominal PK sampling time will be used, for individual participant plots by time, the actual PK sampling time will be used.

These analyses will be carried out with PK concentration analysis set.

6.2. Immunogenicity Analysis

Overall incidence of development of ADA, NAb will be calculated and summarized by treatment and time points specified in the SoA. Participants level immune response will also be summarized by treatment. Effect of positive ADA and neutralizing immune response on safety and PK may be assessed, if appropriate.

6.3. Subset Analyses

Not applicable.

6.4. Baseline and Other Summaries and Analyses

6.4.1. Baseline Summaries

Demographic and baseline characteristics will be summarized descriptively.

6.4.2. Study Conduct and Participant Disposition

A subject disposition table will be provided. Subject disposition will be summarized and will include the number and percentage of participants randomized, treated, completing and discontinuing from the study, the number of participants in each analysis population and reasons for discontinuation of study. The percentages will use the number of randomized as the denominator.

PFIZER CONFIDENTIAL

The official version of this form is located in the electronic document management system.

6.5. Safety Summaries and Analyses

6.5.1. Adverse Events

Adverse events will be reported in accordance with the sponsor reporting standards. Adverse events related to COVID-19 will be summarized.

6.5.2. Laboratory Data

Laboratory data will be summarized using Pfizer's implementation of CDISC standards. Change from baseline will also be summarized by treatment and visit.

Incidence of laboratory test abnormalities (without regard to baseline abnormality) will be summarized.

6.5.3. Vital Signs

Vital signs will be summarized using Pfizer's implementation of CDISC standards. For each planned timepoint, absolute values and change from baseline values will be summarized with descriptive statistics.

Maximum absolute values and maximum change from baseline for vital signs will also be summarized descriptively by treatment using categories. Numbers and percentages of participants meeting the categorical criteria will be provided by treatment and individual values listed.

Categories for Vital Signs

Systolic BP (mm Hg)	min. <90	
Systolic BP (mm Hg) change from baseline	max. decrease ≥ 30	max. increase ≥ 30
Diastolic BP (mm Hg)	min. <50	
Diastolic BP (mm Hg) change from baseline	max. decrease ≥ 20	max. increase ≥ 20

6.5.4. Electrocardiograms

Baseline and changes from baseline for the ECG parameters heart rate, QT interval, QTc interval, PR interval and QRS interval will be summarized by treatment and time.

PFIZER CONFIDENTIAL

The official version of this form is located in the electronic document management system.

The number and percentages of participants with maximum postdose QTc values and maximum increases from baseline in the following categories will be tabulated by treatment:

Safety QTc Assessment

Degree of prolongation	Mild (msec)	Moderate (msec)	Severe (msec)
Absolute value	>450- <480	>480-500	>500
Increase from baseline		30-60	>60

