**Diagnostic Assessments:**

15. A positive urine drug test.
16. Screening supine BP  $\geq 140$  mm Hg (systolic) or  $\geq 90$  mm Hg (diastolic), following at least 5 minutes of supine rest. If BP is  $\geq 140$  mm Hg (systolic) or  $\geq 90$  mm Hg (diastolic), the BP should be repeated 2 more times and the average of the 3 BP values should be used to determine the participant's eligibility.
17. Screening PR  $> 100$  bpm or  $< 50$  bpm. If the PR is greater than 100 bpm or less than 50 bpm, the PR should be repeated 2 more times and the average of the three pulse rate values should be used to determine the participant's eligibility.
18. Baseline standard 12-lead ECG that demonstrates clinically relevant abnormalities that may affect participant safety or interpretation of study results (eg, baseline QTcF interval  $> 450$  msec, complete LBBB, signs of an acute or indeterminate-age myocardial infarction, ST-T interval changes suggestive of myocardial ischemia, second or third-degree AV block, or serious bradyarrhythmias or tachyarrhythmias). If the baseline uncorrected QT interval is  $> 450$  msec, this interval should be rate-corrected using the Fridericia method and the resulting QTcF should be used for decision making and reporting. If QTcF exceeds 450 msec, or QRS exceeds 120 msec, the ECG should be repeated 2 more times and the average of the 3 QTcF or QRS values should be used to determine the participant's eligibility. Computer-interpreted ECGs should be overread by a physician experienced in reading ECGs before excluding a participant.

19. Participants with **ANY** of the following abnormalities in clinical laboratory tests at screening, as assessed by the study-specific laboratory and confirmed by a single repeat test, if deemed necessary:

- AST **or** ALT level  $\geq 1.5 \times \text{ULN}$ ;
- Total bilirubin level  $\geq 1.5 \times \text{ULN}$ ; participants with a history of Gilbert's syndrome may have direct bilirubin measured and would be eligible for this study provided the direct bilirubin level is  $\leq \text{ULN}$ .
- Hemoglobin level  $\leq 120 \text{ g/L}$  ( $12.0 \text{ g/dL}$ );
- Platelet count  $\leq 150 \times 10^9/\text{L}$  ( $150,000 \text{ cells/mm}^3$ );
- WBC count of  $\leq 3.0 \times 10^9/\text{L}$  ( $3000 \text{ cells/mm}^3$ );
- ANC  $< 1500 \text{ cells/mm}^3$ ;
- ALC  $< 800 \text{ cells/mm}^3$ ;
- eGFR  $< 90 \text{ mL/min/1.73 m}^2$  based on the CKD-EPI 2009 equation;

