#### 9.3.4.1. Electrocardiogram Analyses

Changes from baseline for the ECG parameters QT interval, heart rate, QTc interval, PR interval, and QRS complex will be summarized by treatment and time.

The number (%) of participants with maximum post dose QTc values and maximum increases from baseline in the following categories will be tabulated by treatment:

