### Safety QTc Assessment

Degree of Prolongation	Mild (msec)	Moderate (msec)	Severe (msec)
Absolute value	>450-480	>480-500	>500
Increase from baseline		30-60	>60

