## 10.6. Appendix 6: ECG Findings of Potential Clinical Concern

ECG Findings That May Qualify as AEs

• Marked sinus bradycardia (rate <40 bpm) lasting minutes.

• New PR interval prolongation >280 msec.

• New prolongation of QTcF to >480 msec (absolute) or by <math>\geq 60</math> msec from baseline.

• New-onset atrial flutter or fibrillation, with controlled ventricular response rate: ie, rate <120 bpm.

• New-onset type I second-degree (Wenckebach) AV block of >30 seconds' duration.

• Frequent PVCs, triplets, or short intervals (<30 seconds) of consecutive ventricular complexes.

ECG Findings That May Qualify as SAEs

• QTcF prolongation >500 msec.

• New ST-T changes suggestive of myocardial ischemia.

• New-onset left bundle branch block (QRS >120 msec).

• New-onset right bundle branch block (QRS >120 msec).

• Symptomatic bradycardia.

• Asystole:

• In awake, symptom-free participants in sinus rhythm, with documented periods of asystole <math>\geq 3.0</math> seconds or any escape rate <40 bpm, or with an escape rhythm that is below the AV node.

• In awake, symptom-free participants with atrial fibrillation and bradycardia with 1 or more pauses of at least 5 seconds or longer.

• Atrial flutter or fibrillation, with rapid ventricular response rate: rapid = rate >120 bpm.

• Sustained supraventricular tachycardia (rate >120 bpm) (“sustained” = short duration with relevant symptoms or lasting >1 minute).

- Ventricular rhythms >30 seconds' duration, including idioventricular rhythm (heart rate <40 bpm), accelerated idioventricular rhythm (HR >40 bpm to <100 bpm), and monomorphic/polymorphic ventricular tachycardia (HR >100 bpm [such as torsades de pointes]).
- Type II second-degree (Mobitz II) AV block.
- Complete (third-degree) heart block.

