2. INTRODUCTION

This statistical analysis plan (SAP) provides the detailed methodology for summary and statistical analyses of the data collected in Study C0251007. This document may modify the plans outlined in the protocol; however, any major modifications of the primary endpoint definition or its analysis will also be reflected in a protocol amendment.

PFIZER CONFIDENTIAL

The official version of this form is located in the electronic document management system.

The purpose of this study is to evaluate the single-dose PK, safety, and tolerability of PF-06823859 after single IV administration to healthy adult Chinese participants. The information of PK, safety, and tolerability in healthy Chinese participants is being collected to support future PF-06823859 clinical development as well as drug registration in China.

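### SAP 6.5.4 leaves a maximum QTc of exactly 480 msec in no absolute-value category, where the protocol counts it as Mild (minor)

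*SAP*

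**What the plan says.** Both documents plan the same tabulation. Protocol 9.3.4.1 counts participants with "maximum post dose QTc values and maximum increases from baseline in the following categories will be tabulated by treatment", and SAP 6.5.4 counts those with "maximum postdose QTc values and maximum increases from baseline in the following categories will be tabulated by treatment". The bands that follow, under the heading "Degree of Prolongation" in the protocol, are:

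| Row | Document | Mild (msec) | Moderate (msec) | Severe (msec) |
|---|---|---|---|---|
| Absolute value | Protocol 9.3.4.1 | >450-480 | >480-500 | >500 |
| Absolute value | SAP 6.5.4 | >450 to <480 | >480-500 | >500 |
| Increase from baseline | Both | none | 30-60 | >60 |

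Only the Mild absolute cell differs. SAP 3.4 states that the ECG baseline "is defined as the latest measurement prior to taking dose".

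**The concern.** In the SAP the Mild band stops short of 480 and the Moderate band starts above it, so the value 480 belongs to neither. The SAP table is what will be programmed, and ECGs are a named part of the primary safety endpoint. Followed literally, the two documents can give different Mild counts from the same data. The groups are small: about 10 active and 2 placebo participants are planned. One uncounted participant is 1/10 = 10% of the active group or 1/2 = 50% of the placebo group in that cell.

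The SAP does reserve the right to depart from the protocol ("This document may modify the plans outlined in the protocol"). However, its version history lists only the Section 2.2 change on enrolling additional participants, and the protocol's amendment table lists no change to the QTc categories. A deliberate change would also be unlikely to leave a hole between two adjacent bands.

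**Working it through.** There is no sample size, power or error rate to reproduce here, so the check is a direct classification of values. Two reading assumptions apply: QTc is recorded in whole msec, and a band printed as a-b includes its upper end.

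**Absolute-value row.** Each whole value from 451 to 600 msec was placed in the bands of each document.

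| | Protocol | SAP |
|---|---|---|
| Mild values | 451 to 480: 480 − 450 = 30 values | 451 to 479: 479 − 450 = 29 values |
| Moderate values | 481 to 500: 20 values | 481 to 500: 20 values |
| Total assigned, 451 to 500 | 30 + 20 = 50 of 50 | 29 + 20 = 49 of 50 |
| Values in no band | none | 480 |
| Values in two bands | none | none |

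The two tables disagree at 480 and nowhere else.

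**Increase-from-baseline row.** This row is the same in both documents. For a maximum of 480 msec, the increase is 480 minus baseline:

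| Baseline (msec) | Increase (msec) | Category in this row |
|---|---|---|
| 419 or less | 480 − 419 = 61 or more | Severe |
| 420 to 450 | 480 − 420 = 60 down to 480 − 450 = 30 | Moderate |
| 451 to 480 | 480 − 451 = 29 down to 480 − 480 = 0 | none |

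A participant at 480 is therefore missing from the absolute row under the SAP in every case, and from the whole table only if the baseline is 451 to 480.

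**Can such a baseline occur?** It can, reading QTc as QTcF (neither table names the correction). Under Exclusion Criterion 18 in protocol 5.2, when QTcF exceeds 450 msec "the ECG should be repeated 2 more times and the average of the 3 QTcF or QRS values should be used" for eligibility. The SAP baseline, in contrast, is the single latest pre-dose reading. As an illustration with assumed readings, take Day -1 QTcF values of 455, 440 and 452:

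- Eligibility value: (455 + 440 + 452) / 3 = 1347 / 3 = 449, which is not above 450.
- SAP baseline: 452, the last reading.
- Increase at a maximum of 480: 480 − 452 = 28, below the 30 msec threshold.

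The SAP counts this participant in no row; the protocol counts the participant as Mild. This shows only that the case is possible. It says nothing about how likely it is.

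**With the correction.** If the SAP Mild band is >450 to ≤480, every whole value from 451 to 600 falls in exactly one band.

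**The case against.** The strongest objection is that the gap rests on one character in text read from a PDF. The SAP's <480 may be a ≤480 that lost its underline. The ≥ signs do survive in the SAP's vital-signs table just before, but that is a different symbol, and no ≤ sign appears elsewhere in the SAP text to test against. This stands as a caveat: the finding is about the text as printed, and a look at the source file would settle it.

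The case of a participant in neither row needs several things together: a first reading above 450, an average of 450 or less, a last reading above 450, and a post-dose maximum of exactly 480. That is fair, and it is why no likelihood is claimed. It does not repair the absolute row, which omits 480 whatever the baseline.

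Protocol Appendix 6 ("New prolongation of QTcF to" above 480 msec) fits the protocol's table, but it fits the SAP's Moderate band equally well. It does not say where 480 itself belongs, so it cannot decide between the tables.

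The impact is also limited. The SAP states that "No formal statistical tests will be performed", and ECG values are summarised by treatment and time as well, so a reading of 480 still enters those summaries. The ECG monitoring triggers in protocol 8.2.4 do not use this table. All of this is correct, and it supports the minor rating.

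**Conclusion.** The point holds, as a minor one. As printed, SAP 6.5.4 has a gap at exactly 480 msec that protocol 9.3.4.1 does not have, and the difference is not documented as intended. One whole-msec value of the 50 from 451 to 500 is affected. The consequence is a possible undercount of the Mild category in one descriptive safety table, with no effect on PK results or on any inference. The conclusion assumes that the < sign is printed as such in the source file. The counts assume whole-msec recording; with fractional values, only a maximum of exactly 480 is affected.

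**What to change.** In the Safety QTc Assessment table of SAP 6.5.4, print the Mild absolute band as >450 to ≤480 msec. This matches protocol 9.3.4.1 and closes the gap below the Moderate band. It changes one table cell, needs no new data and has no downside. If the source file already shows ≤480, no edit is needed beyond confirming that the table program includes 480 in Mild.
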